1.5 DOSE RATIONALE

Patients enrolled in this study were initially administered subcutaneous (SC) fitusiran once every month where 1 month has been defined as 30 days to aid in patient compliance with the long-term dosing regimen. Patients started the study on weight-based doses then transitioned early on to a 50 mg- or 80 mg-fixed monthly dose depending on what they received in the parent study.

A once-monthly dosing regimen is supported by preliminary results from clinical and nonclinical studies. Data from the parent study (ALN-AT3SC-001) suggest that a reduction in AT levels is sustained for up to 60 days following a single dose of fitusiran. Additionally, preliminary data in nonhuman primates suggest that steady-state AT suppression can be achieved and maintained after monthly doses of fitusiran.

A change in the fitusiran dosing regimen has been introduced as a risk mitigation measure for vascular thrombotic events in Protocol Amendment 07. As the risk of vascular thrombotic events is thought to be increased in the setting of low AT activity levels, a reduced dose of 50 mg administered SC once every 2 months has been selected to minimize the occurrence of AT activity levels below 10%. At a reduced dose of 50 mg every 2 months, if a patient has more than 1 AT level <15%, the patient will be required to permanently discontinue fitusiran. Patients previously exposed to fitusiran at a dose of 50 mg monthly or 80 mg monthly with no more than 1 AT activity level <15% at any time during fitusiran treatment (based on at least 3 months of prior AT measurements) may have the option to remain on either dose, respectively.

If a patient receiving fitusiran 50 mg once every 2 months has 2 steady state AT levels above 35%, the patient will be dose escalated to fitusiran 50 mg monthly. In very rare cases, if a patient still has 2 steady state AT levels above 35% at the 50 mg monthly dose, the patient will escalate to the 80 mg monthly dose. Details are described in Section 6.5.1.3.

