5.3 MANAGEMENT OF BLEEDING EPISODES WITH FACTOR OR BYPASSING AGENTS WHILE ON FITUSIRAN

Investigators will establish and provide instructions for an individualized bleed management plan based on the guidelines in Table 8 for each patient.

The bleed management plan should be reviewed by the Investigator or designee with the patient at each dosing (and via telephone contact every 2 weeks [±4 days] between fitusiran dosing) and updated as necessary.

Initiation of fitusiran treatment results in a progressive lowering of AT levels over 4 weeks.

Guidelines are provided below for patients newly initiating therapy or re-initiating therapy, and during continuous therapy with fitusiran.

Bleed management guidelines for patients with AT recovery of ≥60% prior to re-initiation of fitusiran or during a potential fitusiran dose pause

AT recovery is defined as AT activity level of approximately 60% or greater (per the central laboratory).

After initiating therapy with fitusiran, it is recommended that patients call the Investigator prior to dosing with factor or BPA, and must call for any repeat doses of FVIII, FIX, aPCC, or for the third or subsequent dose of rFVIIa.

As quickly as 7 days after the initial fitusiran dose, the majority of patients will have AT levels at or below 60% residual activity. By 14 days after dosing, it is expected that 94% of participants will have AT activity lowering of >50%, with a median value of 66.8%. Based on these AT kinetics, it is recommended that patients continue with their standard factor/BPA regimens for the first week following re-initiation of fitusiran dosing, with institution of the protocol-specific bleed management guidelines with reduced factor/BPA starting the second week after re-initiation, as described below and in Table 8.

During the study period, in case fitusiran is on pause for any reason and AT activity levels return to approximately 60% (per the central laboratory), patients can initiate regular factor concentrates or BPAs for prophylaxis therapy to prevent spontaneous bleeding episodes, per Investigator discretion in consultation with the study Medical Monitor.

Bleed management guidelines for Week 2 and beyond, and for patients with AT recovery of <60% prior to re-initiation of fitusiran:

When a patient experiences symptoms that may be consistent with bleeding episodes, the following steps should be followed:

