2 STUDY OVERVIEW

2.1 SYNOPSIS OF STUDY DESIGN

LTE14762 is an open-label extension (OLE) study to evaluate long-term safety, tolerability, and efficacy of subcutaneously administered fitusiran in patients with moderate or severe hemophilia A or B, with or without inhibitory antibodies to factor VIII or factor IX, who previously tolerated dosing in the parent study, TDR14767(formerly ALN-AT3SC-001). The primary objective of this study is to evaluate the long-term safety and tolerability of fitusiran, assessed by incidence, severity, relatedness, and seriousness of adverse events, and laboratory assessments.

TDR14767(ALN-AT3SC-001) was a Phase 1 study that evaluated the safety, tolerability, and PK of fitusiran in healthy male volunteers and male patients with hemophilia A or B.

TDR14767(ALN-AT3SC-001) was conducted in 4 parts:

Part A: a randomized, placebo-controlled, single-blind single-ascending dose (SAD) phase in healthy subjects

Part B: an open-label, multiple-ascending dose (MAD) phase in patients with moderate to severe hemophilia A or B without inhibitors

Part C: an open-label, exploratory multiple dose (MD) phase in patients with moderate to severe hemophilia A or B without inhibitors

Part D, an open-label MD phase in patients with moderate to severe hemophilia A or B with inhibitors.

Study TDR14767(ALN-AT3SC-001) was completed on 20 July 2017 (last patient last visit).

Patients who received all 3 doses of study drug in TDR14767(ALN-AT3SC-001) and completed required study visits in the parent study were eligible for participation in LTE14762. All enrolled participants will initially receive a 50 mg or 80 mg dose of fitusiran once monthly.

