Imputation rule for AE is updated in Section 5.8.	Align with Sanofi standard.
Inclusion of analysis window for revised dose and regimen.	Describe the analysis window for revised dose and regimen.
Specify analysis in general will be performed under original dose and regimen and under revised dose and regimen separately in Section 6. Describe planned analysis under revised dose and regimen.	To better evaluate the safety and long-term efficacy of revised dose and regimen.
Describe analysis for dosing interruption periods in Section 6.5.	To evaluate the AT recovery and bleeding during dosing pause in 2017 clinical hold and 2020 voluntary dose pause.
Describe algorithm of identifying cholecystitis and cholelithiasis in Section 6.8.2.	Align with other studies of fitusiran.
Describe analysis of liver function in Section 6.8.3	Additional analysis of liver function.
Description of subgroups to be analyzed in Section 6.11.	Inclusion of subgroups to be analyzed. Given the extended duration of treatment post TDR14767(ALN-AT3SC-001), the treatment type before parent study entry has limited impact on efficacy evaluation. Subgroup analysis of treatment type before enrollment into TDR14767(ALN-AT3SC-001) will be removed.

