We also define Study Days in the LTE14762 study as the number of days from first significant dose in LTE14762 and calculate similarly as the Treatment Days. For participants who received first significant dose in LTE14762, the Study Days is the same as the Treatment Days.

For participants under the revised dose and regimen, both efficacy and safety data will be analyzed from the dose re-start Day 1 up until the last day of study follow-up.

Treatment day after the dose re-start will be calculated as evaluation date – first dose date after dose re-start + 1 (days). It should be not applicable for assessments before the dose re-start. A summary of study periods and start day in analysis is outlined in [Figure 1](#)

Figure 1 Study periods and analysis start day summary

	Original dose and regimen	2017 clinical hold/2020 voluntary dose pause	Revised dose and regimen
Efficacy analysis	Starts from first significant dose of fitusiran in TDR14767(ALN-AT3SC-001) or LTE14762 and in terms of treatment days.	Starts from the 29th days after last dose date before the hold/pause	Starts from first dose date of revised dose and regimen and in terms of treatment days
Safety analysis	Starts from first significant dose of fitusiran in LTE14762 and in terms of study days	Starts from the day after last dose date before the hold/pause and in terms of study days	Starts from first dose date of revised dose and regimen and in terms of study days

Summary statistics will be reported by analysis visits defined in [Section 5.10](#) below. Unless otherwise noted, tables under both the original and revised dose regimens will be presented by hemophilia type, inhibitor type and overall. Participants who received a significant dose in TDR14767(ALN-AT3SC-001) will be considered as a subgroup in the analysis under the original dose and regimen. Details will be specified in the [Section 6.11](#).

Categorical data summary will include the number and percentage of participants within each category, with a category for missing data. Continuous data summary will include descriptive statistics - the number of participants, mean, median, standard deviation (SD), first quartile (Q1), third quartile (Q3), minimum, and maximum. The precision of the measurement for each continuous variable will be used to determine the number of decimal places to present in tables, figures and derived listings. Minimum and maximum values will be reported with the same

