6.5 ANALYSES DURING DOSE INTERRUPTION

For participants who had clinical hold in 2017, the following exploratory analyses will be performed:

Rate of AT recovery since last dose before interruption will be summarized descriptively. AT activity over time since last dose before interruption will be plotted.

AT activity and peak TG over time since last dose before interruption will be plotted.

ABR before, during and after the interruption period will be summarized descriptively. Similarly, maximum bleed free duration for treated bleeding events before and after interruption period will be summarized descriptively. ABR and maximum bleed free duration before and after the interruption period will be analyzed based on efficacy period and on-treatment strategy considering all intercurrent events. Bleeding events during the first 29 days after dose resumption will not be considered based on on-treatment strategy for participants whose 2017 dose hold period >84 days as outlined in [Section 6.3](#). ABR during the interruption period will consider intercurrent events II – V based on on-treatment strategy. The interruption period will start from 29 days after last dose before interruption till the day before first dose at resumption of treatment.

ABR before, during and after the interruption period will be summarized descriptively. Similarly, maximum bleed free duration for all bleeding events before and after interruption period will be summarized descriptively. ABR and maximum bleed free duration before and after the interruption period will be analyzed based on efficacy period and on-treatment strategy considering all intercurrent events. Bleeding events during the first 29 days after dose resumption

will not be considered based on on-treatment strategy for participants whose 2017 dose hold period >84 days as outlined in [Section 6.3](#). ABR during the interruption period will consider intercurrent events II – V based on on-treatment strategy. The interruption period will start from 29 days after last dose before interruption till the day before first dose at resumption of treatment.

For participant who had voluntary dose pause interruption in 2020, similar analysis will be done for the AT/TG assessments, ABR and maximum bleed free duration.

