6.8.1 Study drug exposure

Duration of exposure (years) and the number of study drug doses used from Treatment Day 1 in the TDR14767(ALN-AT3SC-001)/LTE14762 under the original dose and regimen will be summarized descriptively, where duration of exposure (days) = date of the last dose of study drug – the date of the first significant dose of study drug + 28 days excluding the gaps between TDR14767(ALN-AT3SC-001)/LTE14762 and dose suspension in LTE14762. Duration of exposure and the number of study drug doses in LTE14762 study will be summarized similarly.

Duration of exposure under the revised dose and regimen will be summarized. If participant had the last dose under the Q2M dose frequency, the duration (days) = date of the last dose of fitusiran – the date of the first dose of fitusiran under the revised dose and regimen + 56 days. If participant had the last dose under the QM dose frequency, the duration (days) = date of the last dose of fitusiran – the date of the first dose of fitusiran under the revised dose and regimen + 28 days.

The overall duration of exposure regardless of revised dose from the first significant dose and/or from the first dose in the LTE14762 study until the end of study may also be summarized as needed. The planned dose intermittent period ([Table 4](#)) will be excluded from the overall duration of exposure.

Table 4 – Definition of planned dose intermittent periods

	Start date	End date	Note
Gap between parent and extension study	Last fitusiran dose date in parent study + 29 days	First fitusiran dose date in extension study – 1	If duration < 14 days, then no gap between the 2 studies.
2017 dose suspension	Last fitusiran dose before 01SEP2017 + 29 days	First fitusiran dose after 01SEP2017 – 1	If duration < 14 days, then no dose suspension period should be excluded.
2020 dose suspension	Last fitusiran dose date before 31Oct2020 + 29 days	First fitusiran dose after 26Jan2021 – 1	If duration < 14 days, then no dose suspension period should be excluded

Note: Duration is calculated as end date – start date +1 for each dose intermittent periods.

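### The exploratory bleeding rate during dose interruptions starts 29 days after the last dose, so it can include time with antithrombin still lowered and tends to understate bleeding off fitusiran

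*SAP*

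**What the plan says.** SAP 6.5 sets the window for the ABR during an interruption: "The interruption period will start from 29 days after last dose before interruption till the day before first dose at resumption of treatment". The rule is given for the 2017 clinical hold, once for treated bleeds and once for all bleeds. It carries over to the later pause: "For participant who had voluntary dose pause interruption in 2020, similar analysis will be done for the AT/TG assessments, ABR and maximum bleed free duration". Figure 1 in SAP 5.2 gives the same efficacy start for both interruptions: "Starts from the 29th days after last dose date before the hold/pause". Only intercurrent events II to V (surgery and trauma, antithrombin treatment, emicizumab) are considered within this window. No washout, antithrombin (AT) threshold or split by AT level is specified.

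The stated reason for the analysis, in SAP 2.6, is "To evaluate the AT recovery and bleeding during dosing pause in 2017 clinical hold and 2020 voluntary dose pause". SAP 6.5 accordingly also summarizes and plots AT recovery since the last dose, but separately from the ABR.

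On how long the effect lasts, Protocol 1.5 reports from the parent study that "a reduction in AT levels is sustained for up to 60 days following a single dose of fitusiran". Protocol 5.3 sets the recovery level: "AT recovery is defined as AT activity level of approximately 60% or greater (per the central laboratory"). Under Protocol 6.5.1.3, restart after the 2020 pause requires a central-laboratory AT of at least 22%.

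**The concern.** Day 29 follows from the monthly dosing interval and not from AT recovery. It is the day after the on-treatment window closes, at last dose plus 28 days. By the protocol's own figure, AT may still be lowered for another month after that. Restart is possible at an AT well below the recovery level, so some participants may spend their whole window without recovering.

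The SAP is also not consistent with itself here. For participants dosed every 2 months, the exclusions in SAP 6.3 for missed doses and for discontinuation begin at last dose plus 57 days, and the exposure formula in SAP 6.8.1 adds 56 days to the last dose. Days 29 to 56 after a 50 mg dose thus count as on-treatment in one place. After the same or a larger monthly dose they count as interruption in another.

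Wash-in and wash-out are handled differently too. For holds longer than 84 days, the on-treatment analysis discards the early days after resumption, but nothing comparable is removed at the start of the interruption.

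In a single-arm study, readers will take a before/during/after table as evidence of bleeding on and off the drug. Carry-over pulls the middle figure toward the on-treatment rate and shrinks the contrast, by an amount that depends on how long each participant was off drug.

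**Working it through.** The documents give no interruption ABR to reproduce, so the check is day arithmetic.

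**Inputs**

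- Window: last dose + 29 days to the day before resumption (SAP 6.5, Figure 1 in SAP 5.2).
- Dosing before the interruptions was monthly: "All enrolled participants will initially receive a 50 mg or 80 mg dose of fitusiran once monthly" (SAP 2.1).
- Possible carry-over: to Day 60 (Protocol 1.5), or to Day 56 on the SAP's own convention for dosing every 2 months (SAP 6.3, 6.8.1).
- 2020 cut-offs from SAP Table 4: the start is "Last fitusiran dose date before 31Oct2020 + 29 days", and resumption is the first dose after 26 Jan 2021. Table 4 belongs to the exposure analysis. The matching dates in SAP 6.3 are redacted, so I assume the same cut-offs apply.
- Assumed, not in the documents: bleed reduction p during carry-over, 50% to 90%.

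**Formulas.** Let G be the days from last dose to first resumed dose.

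- Window length = (G − 1) − 29 + 1 = G − 29.
- Carry-over days = 60 − 29 + 1 = 32. Share f = 32/(G − 29).
- Pooled ABR ÷ off-drug ABR = f(1 − p) + (1 − f) = 1 − fp, so the understatement is fp.
- If protection falls linearly from p to zero by Day 60, its average is p/2 and the understatement is about fp/2.
- On the Day 56 convention, carry-over days = 56 − 29 + 1 = 28 and the share is 28/(G − 29).

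**Shortest 2020 gap.** From 30 Oct 2020 to 27 Jan 2021 is G = 89. The window is 60 days and f = 32/60 = 53%. The understatement is 0.533 × 0.5 = 27% to 0.533 × 0.9 = 48%. The other gaps in the table are illustrative.

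| G (days) | Window | Days 29–60 share | Understatement, p = 50–90% | With linear waning | Days 29–56 share |
|---|---|---|---|---|---|
| 89 | 60 | 53% | 27–48% | 13–24% | 47% |
| 119 | 90 | 36% | 18–32% | 9–16% | 31% |
| 180 | 151 | 21% | 11–19% | 5–10% | 19% |
| 365 | 336 | 10% | 5–9% | 2–4% | 8% |

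A part starting at Day 61 keeps G − 61 days: 28, 58, 119 and 304 days for the four gaps.

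The formulas take bleeding after Day 60 as the full off-drug rate. If AT stays low for longer after repeated dosing, the understatement is larger. If the effect fades before Day 60, it is smaller.

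**The case against.** Five points can be made in favor of the plan.

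1. **Day 29 is deliberate.** It leaves neither gap nor overlap with the on-treatment window under monthly dosing, and it agrees with Figure 1 and Table 4. This stands, and is a reason to keep the window and add to it.
2. **The size is uncertain.** The 60-day figure is an upper value from single-dose data that the protocol describes only as suggestive. Constant protection to Day 60 is an assumption, and 53% needs both dates at their limits. This stands, which is why the waning case and longer gaps are shown.
3. **The analysis is exploratory and descriptive.** It does not feed the primary safety objective, and the primary on-treatment ABR excludes qualifying interruption time. This stands and limits severity.
4. **An AT split does not yield a clean untreated rate.** Protocol 5.3 allows factor or bypassing-agent prophylaxis in a pause once AT is about 60%. Prophylaxis is not among events II to V, so it can lower the ABR in exactly that stratum. This stands, and the fix has to show such time separately.
5. **AT may be too sparse.** From Year 3, scheduled sampling in Protocol Tables 1 and 2 is largely six-monthly, and no pause-specific schedule appears. This stands, so the main split should be by time since last dose.

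None of these removes the overlap between the window and the period of possible AT lowering.

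**Conclusion.** The point holds at modest severity. The pooled ABR for the interruption combines possible carry-over time with later time, and carry-over biases it downward as an estimate of bleeding off fitusiran. The bias could be substantial in short pauses and is small in long ones: 27% to 48% at 89 days, 11% to 19% at 180 days and 5% to 9% at one year. These figures rest on the assumed 50% to 90% reduction through Day 60, and roughly halve under linear waning. Which gap length applies is unknown, because the documents do not give actual pause lengths.

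Three stronger readings are tempting, but the documents do not support them.

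- **That this is the study's only within-participant contrast for bleeding.** Protocol 10.2.3 also plans bleed-rate reduction against pretreatment, and SAP 6.2 carries a historical ABR.
- **That the SAP sets out to relate bleeding to AT recovery and fails.** SAP 2.6 names both as things to evaluate and states no relation between them. The SAP also never labels the pooled figure an off-drug rate.
- **That the two interruptions differ in length and so cannot be compared.** The dates in SAP 6.3 are redacted, Table 4 gives the same cut-off date for both ends of the 2017 hold, and no comparison of the two is planned.

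**What to change.** Keep the Day 29 window in SAP 6.5 for continuity and add the following, for treated bleeds and for all bleeds:

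- bleed counts, person-days and ABR split by time since last dose, Days 29 to 60 versus Day 61 onward;
- the same split by AT below versus at or above about 60%, where central-laboratory values allow;
- time on factor or bypassing-agent prophylaxis shown separately within each part;
- a sentence saying that the pooled figure is not to be interpreted as the bleeding rate off fitusiran.

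The cost is some SAP wording and a few rows in a descriptive table. Dose dates, bleeds, concomitant medication and AT values are already collected. The downside is fewer days per stratum (28 days after Day 60 in the shortest 2020 pause) and sparse AT values for some participants, so counts and person-days should always accompany the rates.

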6.6 ADDITIONAL EXPLORATORY ANALYSES

For participants who undergo operative procedures during the study, the total number of participants in each rating category of hemostatic efficacy response (“none,” “moderate,” “good,” and “excellent”) will be summarized at each time point for both the intraoperative and postoperative assessments. Other data on surgical cases, including factor/BPA use, may be described in narrative form.

6.7 PHARMACOKINETIC ANALYSIS

Pharmacokinetic analyses will be conducted using the PK analysis set 1 and PK analysis set 2. Plasma PK parameters will be estimated using a population PK approach. The population PK analysis will be described in a separate population PK analysis plan. In addition to performing population PK 32onhealt, PK parameters will also be estimated using non-compartmental analysis in participants who opted to participate in extensive PK sampling during one or more of the PK sampling periods (Day 1, Month 12, Month 24).

PK parameters to be estimated using non-compartmental analysis will include, but will not be limited to: maximum plasma concentration (C_{max}), time to maximum plasma concentration (t_{max}), elimination half-life ($t_{1/2\beta}$), area under the concentration-time curve (AUC), apparent clearance (CL/F), and apparent volume of distribution (V/F). The amount of fitusiran excreted in 0-24 h urine from a subset of participants who opted to participate in urine collections, will also be estimated using non-compartmental analysis. Other plasma and/or urine PK parameters may also be calculated, if considered appropriate.

